8.1.2 Laboratory test abnormalities

8.1.2.1 Definitions and reporting

Laboratory abnormalities that constitute an Adverse event in their right (are considered clinically significant, induce clinical signs or symptoms, require concomitant therapy or require changes in study treatment), should be recorded on the Adverse Events CRF. Whenever possible, a diagnosis, rather than a symptom should be provided (e.g. anemia instead of low hemoglobin). Laboratory abnormalities that meet the criteria for Adverse Events should be followed until they have returned to normal or an adequate explanation of the abnormality is found. When an abnormal laboratory or test result corresponds to a sign/symptom of an already reported adverse event, it is not necessary to separately record the lab/test result as an additional event.

Laboratory abnormalities, which do not meet the definition of an adverse event, should not be reported as adverse events. A Grade 3 or 4 event (severe) as per CTCAE does not automatically indicate a SAE unless it meets the definition of serious as defined below and/or as per investigator's discretion. A dose hold or medication for the lab abnormality may be required by the protocol in which case the lab abnormality would still, by definition, be an adverse event and must be reported as such.

8.1.3 Adverse events of special interest

Adverse events of special interest (AESI) are defined as events (serious or non-serious) which are ones of scientific and medical concern specific to the sponsor's product or program, for which ongoing monitoring and rapid communication by the investigator to the sponsor may be appropriate. Such events may require further investigation to characterize and understand them.

Adverse events of special interest are defined by an ongoing review of the safety data. AESIs are discussed in detail in the Investigator Brochure.

The AESIs for this study are:

- Bleeding events
- Hepatobiliary events
- Renal related events
- Cataract-related events
- Thromboembolic events
- Hematological malignancy
- Abnormal bone marrow analysis/cytogenetic abnormality

8.2 Serious adverse events

8.2.1 Definitions

Serious adverse event (SAE) is defined as one of the following:

- Is fatal or life-threatening

- Results in persistent or significant disability/incapacity
- Constitutes a congenital anomaly/birth defect
- Is medically significant, i.e., defined as an event that jeopardizes the patient or may require medical or surgical intervention to prevent one of the outcomes listed above
- Requires inpatient hospitalization or prolongation of existing hospitalization,
- Note that hospitalizations for the following reasons should not be reported as serious adverse events:
 - Routine treatment or monitoring of the studied indication, not associated with any deterioration in condition
 - Elective or pre-planned treatment for a pre-existing condition that is unrelated to the indication under study and has not worsened since signing the informed consent
 - Social reasons and respite care in the absence of any deterioration in the patient's general condition
- Note that treatment on an emergency outpatient basis that does not result in hospital admission and involves an event not fulfilling any of the definitions of a SAE given above is not a serious adverse event

8.2.2 Reporting

To ensure patient safety, every SAE, regardless of suspected causality, occurring after the patient has provided informed consent and until at least 30 days after the patient has stopped study treatment must be reported to Novartis within 24 hours of learning of its occurrence.

Any SAEs experienced after these 30 days period should only be reported to Novartis if the investigator suspects a causal relationship to the study treatment. Recurrent episodes, complications, or progression of the initial SAE must be reported as follow-up to the original episode within 24 hours of the investigator receiving the follow-up information. An SAE occurring at a different time interval or otherwise considered completely unrelated to a previously reported one should be reported separately as a new event.

Information about all SAEs is collected and recorded on the Serious Adverse Event Report Form; all applicable sections of the form must be completed in order to provide a clinically thorough report. The investigator must assess and record the relationship of each SAE to each specific study treatment (if there is more than one study treatment), complete the SAE Report Form in English, and send the completed, signed form by email ([contact]) within 24 hours to Novartis patient safety department:

The telephone, email or telefax number of the contact persons in the local department of Novartis patient safety, specific to the site, are listed in the investigator folder provided to each site. The original copy of the SAE Report Form and the fax confirmation sheet must be kept with the case report form (CRF) documentation at the study site.

Follow-up information is sent to the same contact(s) to whom the original SAE Report Form was sent, using a new SAE Report Form stating that this is a follow-up to the previously reported SAE and giving the date of the original report. Each re-occurrence, complication, or

progression of the original event should be reported as a follow-up to that event regardless of when it occurs. The follow-up information should describe whether the event has resolved or continues, if and how it was treated, whether the blind was broken or not, and whether the patient continued or withdrew from study participation.

If the SAE is not previously documented in the Investigator's Brochure or Package Insert (new occurrence) and is thought to be related to the Novartis study treatment, an oncology Novartis Drug Safety and Epidemiology (DS&E) department associate may urgently require further information from the investigator for Health Authority reporting. Novartis may need to issue an Investigator Notification (IN), to inform all investigators involved in any study with the same drug that this SAE has been reported. Suspected Unexpected Serious Adverse Reactions (SUSARs) will be collected and reported to the competent authorities and relevant ethics committees in accordance with Directive 2001/20/EC or as per national regulatory requirements in participating countries.

8.3 Pregnancies

Pregnancy, in and of itself, is not regarded as an AE, unless there is a suspicion that the study drug may have interfered with the effectiveness of a contraceptive medication or method.

To ensure patient safety, each pregnancy occurring while the patient (or the partner of male study patients) is on study treatment, should be recorded on a Clinical Trial Pregnancy Form and reported by the investigator to the PhV department of Novartis within 24 hours of learning of its occurrence.

The pregnancy should be followed up to determine outcome, including spontaneous or voluntary termination, details of the birth, and the presence or absence of any birth defects, congenital abnormalities, or maternal and/or newborn complications. Pregnancy follow-up should be recorded on the same form and should include an assessment of the possible relationship to the study treatment any pregnancy outcome. Any SAE experienced during pregnancy must be reported on the SAE Report Form.

Pregnancy outcomes must be collected for the female partners of any males who took study treatment in this study. Consent to report information regarding these pregnancy outcomes should be obtained from the mother

8.4 Warnings and precautions

No evidence available at the time of the approval of this study protocol indicated that special warnings or precautions were appropriate, other than those noted in the provided Investigator Brochure. Additional safety information collected between IB updates will be communicated in the form of Investigator Notifications. This information will be included in the patient informed consent and should be discussed with the patient during the study as needed.

9 Data collection and management

9.1 Data confidentiality

Information about study subjects will be kept confidential and managed under the applicable laws and regulations. Those regulations require a signed subject authorization informing the subject of the following:

- What protected health information (PHI) will be collected from subjects in this study
- Who will have access to that information and why
- Who will use or disclose that information
- The rights of a research subject to revoke their authorization for use of their PHI.

If a subject revokes authorization to collect or use PHI, the investigator, by regulation, retains the ability to use all information collected before the revocation of subject authorization. For subjects that have revoked authorization to collect or use PHI, attempts should be made to obtain permission to collect follow-up safety information (e.g. has the subject experienced any new or worsened AEs) at the end of their scheduled study period.

The data collection system for this study uses built-in security features to encrypt all data for transmission in both directions, preventing unauthorized access to confidential participant information. Access to the system will be controlled by a sequence of individually assigned user identification codes and passwords, made available only to authorized personnel who have completed prerequisite training.

9.2 Site monitoring

Before study initiation, at a site initiation visit or an investigator's meeting, Novartis personnel will review the protocol and CRFs with the investigators and their staff. During the study, the field monitor will visit the site regularly to check the completeness of patient records, the accuracy of entries on the CRFs, the adherence to the protocol to Good Clinical Practice, the progress of enrollment, and to ensure that study treatment is being stored, dispensed, and accounted for according to specifications. Key study personnel must be available to assist the field monitor during these visits.

The investigator must maintain source documents for each patient in the study, consisting of case and visit notes (hospital or clinic medical records) containing demographic and medical information, laboratory data, electrocardiograms, and the results of any other tests or assessments. All information recorded on CRFs must be traceable to source documents in the patient's file. The investigator must also keep the original signed informed consent form (a signed copy is given to the patient).

The investigator must give the monitor access to all relevant source documents to confirm their consistency with the CRF entries. Novartis monitoring standards require full verification for the presence of informed consent, adherence to the inclusion/exclusion criteria and documentation of SAEs. Additional checks of the consistency of the source data with the CRFs are performed according to the study-specific monitoring plan.

9.3 Data collection

The study will be conducted using Electronic Data Capture (EDC). The designated investigator staff will enter the data required by the protocol into the Electronic Case Report Forms (eCRF). The eCRFs have been built using fully validated secure web-enabled software that conforms to 21 CFR Part 11 requirements. Investigator site staff will not be given access to the EDC system until they have been trained. Automatic validation programs check for data discrepancies in the eCRFs and, allow modification or verification of the entered data by the investigator staff.

The Principal Investigator is responsible for assuring that the data entered into eCRF is complete, accurate, and that entry and updates are performed promptly.

9.4 Database management and quality control

Novartis personnel will review the data entered by investigational staff for completeness and accuracy. Electronic data queries stating the nature of the problem and requesting clarification will be created for discrepancies and missing values and sent to the investigational site via the EDC system. Designated investigator site staff are required to respond promptly to queries and to make any necessary changes to the data.

Concomitant treatments and prior medications entered into the database will be coded using the WHO Drug Reference List, which employs the Anatomical Therapeutic Chemical classification system. Medical history/current medical conditions and adverse events will be coded using the Medical dictionary for regulatory activities (MedDRA) terminology.

Bone marrow aspirate and/or peripheral blood will be processed and analyzed centrally, and the results will be sent to the PI of each site. Each PI will introduce the results into the eCRF.

At the conclusion of the study, the occurrence of any protocol violations will be determined. After these actions have been completed and the data has been verified to be complete and accurate, the database will be declared locked for data analysis. Authorization is required prior to making any database changes to locked data, by joint written agreement between the Global Head of Biostatistics and Data Management and the Global Head of Clinical Development.

For EDC studies, after database lock, the investigator will receive a CD-ROM or paper copies of the patient data for archiving at the investigational site.

10 Statistical methods and data analysis

10.1 Analysis sets

10.1.1 Full Analysis Set

The Full Analysis Set (FAS) comprises all patients to whom study treatment has been assigned.

10.1.2 Safety Set

The Safety Set includes all patients who received at least one dose of study treatment.

10.1.3 Per-Protocol Set

The Per-Protocol Set (PPS) consists of a subset of the patients in the FAS who are compliant with requirements of the clinical study protocol (CSP).

Oncology standards for protocol deviations **potentially** leading to exclusion from the PPS are:

- If the protocol deviation is very likely to confound the scientific analysis of the primary efficacy endpoint(s) or if it precludes any meaningful efficacy measurement.
- If it is in direct conflict with the analysis set definition given in the title of the study (i.e. patient diagnosis, stage of disease or use of prior treatment dose not correspond to the intended patient population to be studied).
- If documentation of pre-baseline disease progression is required and is missing.
- Treatment differs from treatment assigned.
- Patient compliance is defined as patient being evaluated for primary efficacy endpoint at least once. Patients who discontinue prior to the first efficacy assessment due to adverse events, including death, will be included.

Any other deviation leading to exclusion from the PPS will be specified in the study Statistical Analysis Plan (SAP) or DHP.

10.2 Patient demographics/other baseline characteristics

Demographic (age of the patient, sex) and other baseline data (disease characteristics, transplant data by donor type, source of graft cells, conditioning regimen, GVHD prevention regimen, supportive care and infection prophylaxis, other medical history and prior medications will be summarized descriptively for the FAS.

Categorical data will be presented as frequencies and percentages. For continuous data, mean, standard deviation, median, 25th and 75th percentiles, minimum, and maximum will be presented. Categories for missing data will be presented if necessary.

10.3 Treatments (study treatment, concomitant therapies, compliance)

Duration of exposure to study treatment, cumulative dose, average daily dose, actual dose intensity and relative dose intensity of study treatment will be summarized.

Categorical data will be summarized as frequencies and percentages. For continuous data, mean, standard deviation, median, 25th and 75th percentiles, minimum, and maximum will be presented. Safety Set will be used for the analyses.

The number of patients with dose changes/interruptions and their reasons will be summarized on the Safety Set and all dosing data will be listed.

Concomitant medications or procedures and significant non-drug therapies taken concurrently with the study treatment will be listed and summarized using frequency counts and percentages. These summaries will include medications starting on or after the start of study treatment (defined as Day 1) or medications starting before the start of study treatment and continuing after the start of study treatment.

Any prior concomitant medications or significant non-drug therapies starting and ending before the start of study treatment will be listed.

The Safety Set will be used for all of the above mentioned concomitant medication tables and listings.

10.4 Primary objective

The primary objective is to evaluate the efficacy of eltrombopag for poor graft function on overall hematologic response (partial and complete) as determined by platelet, hemoglobin and neutrophil counts, by 16 weeks after the initiation of eltrombopag.

10.4.1 Variable

The primary variable is the overall hematological response (partial and complete) by 16 weeks after the initiation of eltrombopag. The primary analysis will be assessed based on the FAS.

A partial hematologic response (PR) is defined when **any** of the following:

- Platelet count $\geq 20,000/\mu\text{L}$ (with platelet transfusion independence), confirmed in two consecutive blood tests separated a minimum of 7 days.
- Absolute neutrophil count (ANC) $\geq 1,000/\mu\text{L}$ (when pretreatment ANC was $< 1,000/\mu\text{L}$), confirmed in two consecutive blood tests separated a minimum of 7 days.
- Hemoglobin $\geq 100\text{g/L}$ (when pretreatment Hb was $< 100\text{g/L}$) (with red blood cells (RBC) transfusion independence), confirmed in two consecutive blood tests separated a minimum of 7 days.

A complete hematologic response (CR) is defined when **all three** of the following:

- Platelet count $\geq 100,000/\mu\text{L}$, confirmed in two consecutive blood tests separated a minimum of 7 days.
- Absolute neutrophil count (ANC) $\geq 1,500/\mu\text{L}$ (when pretreatment ANC was $< 1,000/\mu\text{L}$), confirmed in two consecutive blood tests separated a minimum of 7 days.
- Hemoglobin $\geq 110\text{ g/L}$ (when pretreatment Hb was $< 100\text{g/L}$), confirmed in two consecutive blood tests separated a minimum of 7 days.

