The increasing of reduced intensity conditioning and wider application of human leukocyte antigen (HLA)-mismatched donors in recent years may have turned graft failure into an increasing problem reported a rate of PGF of 5-27% (Larocca et al., 2006, Xiao et al., 2014) analyzed 124 patients with a median age of 28 years (4-60 years) who underwent an allo-SCT between 2009-2012. Among the 124 patients who received allo-HSCT, 15 experienced PGF (12.1%) with a median follow-up time of 7 months. They identified that patient age, donor-recipient blood-type matching and cytomegalovirus (CMV) infection (in 30 days) were potential risk factors for PGF and suggest that elderly patients or those with incompatible donor-recipient blood matches and/or at high-risk of CMV infection should receive early medical intervention (Xiao et al., 2014).

In the study reported by Sun et al. in 2015 in a series of 464 patients, similar rates were observed, but they also reported that subjects with early PGF have significantly poorer overall survival at 2 years than subjects with good graft function (34.6 vs 87%, p <0.001) (Sun et al., 2015).

Current approaches to treat graft failure and which have been adapted to PGF as well are based on pharmacological and cellular-based treatments. Drugs such as cyclosporine, cyclophosphamide, antithymocyte globulin or mammalian target of Rapamycin (mTOR) inhibitors are used, however these approaches are more useful in the prevention rather than in

the treatment of this complication. The cellular-based approaches include donor lymphocyte infusion (DLIs), regrafting and newer therapies such as infusion of mesenchymal stromal cells. DLIs reduces the risk of graft failure and can restore donor chimerism but can induce severe and sometimes fatal GVHD. Regrafting involves a second HSCT that can successfully rescue a remarkable proportion of patients but with a considerable impact on morbidity and mortality. To date, no single drug or strategy has incontrovertibly proven to be superior to another for reverting graft failure and current approaches are primarily based on its prevention ([Locatelli et al., 2014](#)). New drugs are mandatory to cover this medical need.

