5. Cytogenetic abnormality in chromosome 7 present before the allo-HSC.
6. Evidence of any clonal abnormality on cytogenetics (in bone marrow analysis).
 - A local post-transplant conventional cytogenetic assessment should be available within 8 weeks before Day 1.
 - If the cytogenetics is not valuable, i.e, it does not show metaphases, a FISH for MDS-related most frequent abnormalities including chromosome 7 is accepted.

As a consequence, patients with dry tap bone marrow aspiration are NOT eligible.

7. Evidence of bone marrow involvement or progression of the underlying disease assessed by the applicable methods in each case.
8. Evidence of thrombotic microangiopathy.
9. Evidence of possible causes of cytopenia other than PGF (active infections, myelotoxic drugs, hypersplenism...).
10. Prior use of any thrombopoietin receptor (TPO-R) agonists for PGF.
11. AST or ALT levels $>3 \times$ ULN.
12. Creatinine level $\geq 1.5 \times$ ULN.
13. Total bilirubin level $\geq 1.5 \times$ ULN.
14. Previous thromboembolic event (other than line-related upper extremity thrombosis)
15. Hypersensitivity to eltrombopag or its components.
16. Clinically significant ECG abnormality history or current diagnosis of cardiac disease indicating significant risk of safety for subjects participating in the study such as uncontrolled or significant cardiac disease or impaired cardiac function including any of the following:
 - a). Corrected QTc > 450 msec (male subjects), > 460 msec (female subjects) using Fredericia correction (QTcF) on the screening ECG
 - b). Myocardial infarction
 - c). Uncontrolled congestive heart failure
 - d). Unstable angina
 - e). Congenital long QT syndrome.
17. Administration of an investigational drug within 30 days or 5 half-lives, whichever is longer, preceding the first dose of study treatment.
18. Patient with liver cirrhosis.
19. Risk factors for Torsade de Pointes including uncorrected hypokalemia or hypomagnesemia.

20. Subjects with any serious and/ or unstable pre-existing medical, psychiatric disorder or other conditions that could interfere with patient's safety, obtaining informed consent or compliance with the study procedures as per investigator discretion.

6 Treatment

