6.1.2 Treatment duration

The duration of treatment with eltrombopag will be based on the reasons described below and other reasons for early withdrawal ([Section 7.2.3.17.2.3.1](#)):

- If no partial or complete hematological response is observed at 16 weeks and maintained afterwards, the patient will be withdrawn from the study.
- In patients achieving complete response without transfusion support for a minimum of 8 weeks, the dose of eltrombopag may be reduced by 50%, and discontinued if counts remain stable after 8 weeks at the reduced dose. If relapse occurs after eltrombopag discontinuation, eltrombopag can be reintroduced at the last effective dosage.
- If new clonal cytogenetic abnormalities associated with dysplastic bone marrow findings are observed such as monosomy 7, eltrombopag should be permanently discontinued.

- If the patient develops myelodysplastic syndrome (MDS) or acute myeloid leukemia (AML) assessed by sensitive methods, eltrombopag will be permanently discontinued.
- If other non-clonal and/or cytogenetic abnormalities with uncertain meaning not previously observed and not associated with worsening blood counts or bone marrow dysplastic, the decision of discontinuing eltrombopag is up to the investigator, based on a more frequent bone marrow aspirate monitoring of cytogenetic abnormalities and dysplastic findings.
- If relapse of previous hematological disease occurs, eltrombopag will be permanently discontinued.
- If patient receives a new HSCT, eltrombopag will be permanently discontinued

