6.3.2 Prohibited concomitant therapy

The following medications are prohibited:

- Any other TPO-R agonists are prohibited during this study (e.g., N-plate [romiplostim]).
- Use of corticoids at doses higher than 0.33 mg/kg/day is also prohibited (equivalent doses of prednisone).

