10.4.2 Statistical hypothesis, model, and method of analysis

No hypotheses or models will be considered for these analyses and descriptive statistics will be provided; inferences to the target population (when applicable) will be made using interval estimation.

The proportion of patients who reach the overall response rate (partial and complete) by 16 weeks after the initiation of eltrombopag will be calculated and the corresponding 95% confidence interval (CI). This CI will be one-sided and will be constructed using the relationship between the sums of binomial probabilities and the F distribution described by Clopper and Pearson using the formulas proposed elsewhere (Fleiss JL, Levin B, Paik MC. Statistical Methods for Rates and Proportions. Third edition. John Wiley & Sons: New York, 2003, pp. 25):

$$P_L = \frac{x_0}{x_0 + (n - x_0 + 1)F_{2(n-x_0+1), 2x_0; \alpha}}$$

where $\alpha=0.05$, x_0 is the observed number of responders in the sample and n the sample size.

Descriptive statistics will also be provided between baseline and 16 weeks for blood cell counts (ANC and platelet) and hemoglobin levels, and appropriate paired exploratory tests will be done according to the type of distribution (parametric or not) to assess the statistical significance of the changes.

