### 10.1 Primary objective

**To evaluate the efficacy of eltrombopag for poor graft function on overall hematologic response (partial and complete) as determined by platelets, hemoglobin and neutrophil counts, by 16 weeks after the initiation of eltrombopag.**

It will be calculated:

- The overall response rate, defined as the percentage of patients who have a hematological response (partial and complete) by 16 weeks after the initiation of eltrombopag. If the patient hasn't response in that week because was exit from the study before week 16 and in the last evaluation had a partial or complete response, also be considered as responder.

### 10.2 Secondary objective 1

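### The primary response rule has no provision for other treatment of poor graft function, so the week-16 rate may include recoveries not due to eltrombopag

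*Protocol*

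**What the plan says.** **Endpoint.** Protocol 10.4.1: "The primary variable is the overall hematological response (partial and complete) by 16 weeks after the initiation of eltrombopag". The analysis is on the FAS. A partial response needs only one lineage above its threshold, confirmed on a second consecutive test at least a week later. The partial-response criteria for platelets and hemoglobin also require transfusion independence. No criterion refers to any other treatment for PGF. SAP 10.1 repeats the endpoint as "the percentage of patients who have a hematological response (partial and complete) by 16 weeks after the initiation of eltrombopag". It also counts a patient who leaves before week 16 as a responder if the last evaluation showed a response, whatever the reason for leaving.

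**Other treatments.** Protocol 1.1 describes current options: "The cellular-based approaches include donor lymphocyte infusion (DLIs), regrafting and newer therapies such as infusion of mesenchymal stromal cells". The reference list includes a study of CD34+-selected cell boosts in PGF.

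**Restrictions on study.** Protocol 6.3.2: "Any other TPO-R agonists are prohibited during this study". The only other prohibition there is corticosteroids above a stated dose. Protocol 6.1.2 covers one cell-based treatment: "If patient receives a new HSCT, eltrombopag will be permanently discontinued". Boosts, donor lymphocytes and mesenchymal cells appear in neither list.

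**Handling in the analysis.** Protocol 10.4.3 summarises discontinuations and notes other missing data as missing. Protocol 10.3 lists and summarises concomitant procedures and non-drug therapies without linking them to response. SAP section 4 assigns everything except adverse events to the FAS; the Per-Protocol Set is defined but given no analysis.

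**The concern.** The objective is the efficacy of eltrombopag, in a single arm. There is no comparator in which the effect of other treatments would also appear. The patients most likely to receive a boost or donor cells are those in whom eltrombopag is not working. If their counts then recover by week 16, a drug failure becomes a success. The error runs in one direction only.

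The plan already tries to separate drug effect from other support by requiring transfusion independence for two of the partial-response criteria. It does not carry that idea over to treatments aimed at the graft itself. At stake is the statement in protocol 10.7 that the interval gives evidence of a response proportion above 30%.

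**Working it through.** **1. Does the rule, followed exactly, score such a patient as a responder?** Take a patient with baseline ANC below 1,000/µL and no response by week 6 who then receives a cell boost. Hematology is scheduled at weeks 6, 8, 10 and 12 (protocol 7.2.2.3). ANC of at least 1,000/µL at weeks 10 and 12 gives two consecutive tests about 14 days apart. One lineage is enough, so this is a partial response by week 16 in the FAS. Nothing in 6.1.2 or 6.3.2 stops the drug or the visits, and nothing in 10.4 removes the counts.

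**2. Does the same hold after a new transplant?** Mostly not. Eltrombopag stops permanently (6.1.2), which is a ground for withdrawal (7.2.3.1). A withdrawn patient has one scheduled visit left, 30 days after the last dose (7.2.3). One count cannot make a new confirmed response. It takes unscheduled tests, or a patient who stays on study because withdrawal under 7.2.3.1 is permissive.

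**3. The plan's own figure.** Inputs: n = 33 and an observed 45% (10.7), α = 0.05 (10.4.2), and "This CI will be one-sided". The Clopper-Pearson lower limit is

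P_L = x / [x + (n − x + 1) F], with F the upper 5% point on 2(n − x + 1) and 2x degrees of freedom.

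With x = 0.45 × 33 = 14.85, P_L = 30.1%, at a distance of 14.9 points. This matches Table 10-1.

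**4. Whole patients.**

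| Responders of 33 | Observed | Lower limit |
|---|---|---|
| 13 | 39.4% | 25.1% |
| 14 | 42.4% | 27.8% |
| 15 | 45.5% | 30.5% |
| 16 | 48.5% | 33.3% |
| 17 | 51.5% | 36.1% |

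The limit exceeds 30% from 15 responders upward. Reclassifying one patient takes 15 to 14 and the limit from 30.5% to 27.8%. From 16 it takes two reclassified patients to fall below 30%; from 17 it takes three.

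**5. How often is the result that close?** At a true rate of 45%, P(X ≥ 15) = 54.6% and P(X ≥ 16) = 40.8%, so P(X = 15) = 54.6 − 40.8 = 13.8%.

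**6. Possible size (assumptions, not document figures).** Let the true drug response be 30%. Let a share r of the remaining 70% receive another treatment by week 16, and a share s of those recover. The apparent rate is 0.30 + 0.70 × r × s.

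| r | s | Apparent rate | Extra responders, 33 × 0.70 × r × s | P(X ≥ 15) |
|---|---|---|---|---|
| 0 | – | 30.0% | 0 | 4.4% |
| 3% | 50% | 31.1% | 0.3 | 5.8% |
| 10% | 50% | 33.5% | 1.2 | 10.4% |
| 10% | 80% | 35.6% | 1.8 | 15.8% |
| 20% | 80% | 41.2% | 3.7 | 37.1% |

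**The case against.** The strongest reply is that the problem may never arise. The documents give no frequency, and if nobody receives such treatment by week 16 the rate is unaffected. Protocol 1.1 calls the drug approaches more useful for prevention than for treatment. It credits donor lymphocytes with restoring chimerism, yet entry already requires more than 90% donor chimerism. The boost is not in that section's list and appears only as a reference title. The investigator may withdraw a patient at any time (7.2.3.1), and other therapies would be visible in the listings (10.3). Protocol 10.4.2 states no hypothesis, so 30% is a planning mark and not a decision rule.

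All of this limits the size of the problem, and none of it supplies the missing rule. Withdrawal at discretion is not a scoring rule, and a listing does not change the FAS rate.

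Three stronger readings are tempting, and the documents do not support them:

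- A reader might infer that the primary rate cannot be attributed to eltrombopag. That depends on a frequency nobody has stated.
- A reader might infer that a new transplant readily produces responders. The stop rule and the confirmation requirement leave only the narrow route in step 2.
- A reader might infer that cell therapy shortly before Day 1 is an equal problem, because the exclusion aimed at earlier PGF treatment is "Prior use of any thrombopoietin receptor (TPO-R) agonists for PGF". But counts must still be below threshold on a re-test within 7 days of Day 1 (7.2.1.1), so earlier therapy had not yet worked by then.

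**Conclusion.** The point holds as a gap in the endpoint definition with a known direction and an unknown size. As written, recovery after a boost, donor lymphocytes or mesenchymal cells counts as an eltrombopag response. After a new transplant it counts only through unscheduled tests or in a patient who is not withdrawn. The primary rate may therefore include responses not due to the drug, at 3.0 points per patient.

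A reader might infer that one patient would always overturn the result. One patient moves the limit across 30% only when exactly 15 respond, which has probability 13.8% at a true 45%. The wider range, from 4.4% up to 37.1% for the chance of reaching 15 responders when the true drug rate is 30%, rests entirely on the assumed values of r and s.

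**What to change.** Add the following to protocol 10.4.1 and SAP 10.1, state that it also governs the early-exit clause, and apply it to the week 24 and week 36 responses:

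> Counts on or after the first date of a new HSCT, stem cell boost, donor lymphocyte or mesenchymal cell infusion, or another non-supportive drug started to treat PGF do not count toward response. Permitted G-CSF, EPO and transfusions are not included in this list. A patient without a confirmed response before that date is a non-responder in the primary analysis.

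Report the rate regardless of such treatment as a sensitivity analysis. The exemption is needed because 6.3.1.1 permits G-CSF, EPO and transfusions; without it, starting G-CSF could make a patient a non-responder in every lineage.

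The cost is wording. Protocol 6.3 already requires on-study medications and significant non-drug therapies to be recorded, and the split by start of therapy in 10.3 presupposes start dates. Check that the eCRF takes a date for each cell infusion. I do not propose a sensitivity analysis for cell therapy before Day 1: the look-back in 6.3 is only 30 days before study entry, so the data may not exist.

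The downside is that the reported response rate may be slightly lower. N stays 33. The rule changes only how counts are scored; whether such treatment is allowed remains with the sponsor's clinicians.
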